## **11. REGULATORY AND REPORTING REQUIREMENTS**

Expedited adverse event (AE) reporting for this study is via CTEP-AERS (CTEP Adverse Event Reporting System), accessed via the secure CTEP web site (<https://eapps-ctep.nci.nih.gov/ctepaers>). The reporting procedures to be followed are presented in the “CTEP, NCI Guidelines: Adverse Event Reporting Requirements” which can be downloaded from the *CTEP web site* ([http://ctep.cancer.gov/protocolDevelopment/electronic\\_applications/adverse\\_events.htm](http://ctep.cancer.gov/protocolDevelopment/electronic_applications/adverse_events.htm)).

The descriptions and grading scales found in the revised NCI Common Terminology Criteria for Adverse Events (CTCAE) version 4.0 will be utilized for adverse event reporting. All appropriate treatment areas should have access to a copy of the CTCAE version 4.0. A copy of the CTCAE version 4.0 can be downloaded from the CTEP web site (<http://ctep.cancer.gov>).

A list of adverse events that have occurred or might occur (Comprehensive Adverse Events and Potential Risks list) can be found in [Section 7](#) (Pharmaceutical Information). A copy of the

current Agent-Specific Adverse Event List (ASAEL) is sent with LOI approval letters. The ASAEL is updated periodically; copies of the updated list are available on request via e-mail from [contact].

### 11.1 Expedited Adverse Event Reporting (AE; formerly known as Adverse Drug Reaction)

Expedited reports are submitted to CTEP via the secure CTEP-AERS application accessed via the CTEP web site (<https://eapps-ctep.nci.nih.gov/ctepaers>). Those AEs that do not require expedited reporting must be reported in routine (CDUS) study data submissions. AEs reported through CTEP-AERS must **also** be reported in routine study data submissions. In the rare event when Internet connectivity is disrupted a 24-hour notification is to be made to NCI by telephone at: [contact], or [contact] for CIP studies. An electronic report MUST be submitted immediately upon re-establishment of internet connection. Please note that all paper CTEP-AERS forms have been removed from the CTEP website and will NO LONGER be accepted.

#### 11.1.1 Expedited Reporting Guidelines – Phase 2 studies with investigational agents (including hospitalization defined in bullet 1 below)

#### CTEP-AERS Reporting Requirements for Adverse Events that occur within 30 Days of the Last Dose of the Investigational Agent on Phase 2 and 3 Trials

| Phase 2 and 3 Trials  |                         |                  |              |                                 |                         |                               |                         |                           |                           |
|---|-------------------------|------------------|--------------|---------------------------------|-------------------------|-------------------------------|-------------------------|---------------------------|---------------------------|
|   | Grade 1                 | Grade 2          | Grade 2      | Grade 3                         |                         | Grade 3                       |                         | Grades 4 & 5  | Grades 4 & 5  |
|   | Unexpected and Expected | Unexpected       | Expected     | Unexpected with Hospitalization | without Hospitalization | Expected with Hospitalization | without Hospitalization | Unexpected                | Expected                  |
| Unrelated Unlikely   | Not Required            | Not Required     | Not Required | 10 Calendar Days                | Not Required            | 10 Calendar Days              | Not Required            | 10 Calendar Days          | 10 Calendar Days          |
| Possible Probable Definite   | Not Required            | 10 Calendar Days | Not Required | 10 Calendar Days                | 10 Calendar Days        | 10 Calendar Days              | Not Required            | 24-Hour; 5 Calendar Days  | 10 Calendar Days          |
|  Adverse events with attribution of possible, probable, or definite that occur greater than 30 days after the last dose of treatment with an agent under a CTEP IND require reporting as follows:
CTEP-AERS 24-hour notification followed by complete report within 5 calendar days for: 
 
Grade 4 and Grade 5 unexpected events
 
 CTEP-AERS 10 calendar day report: 
 
Grade 3 unexpected events with hospitalization or prolongation of hospitalization
 
Grade 5 expected events
 
  Although an CTEP-AERS 24-hour notification is not required for death clearly related to progressive disease, a full report is required as outlined in the table. |                         |                  |              |                                 |                         |                               |                         |                           |                           |
| December 15, 2004   |                         |                  |              |                                 |                         |                               |                         |                           |                           |

***Note: All deaths on study require both routine and expedited reporting regardless of causality. Attribution to treatment or other cause must be provided.***

- Expedited AE reporting timelines defined:
  - “24 hours; 5 calendar days” – The investigator must initially report the AE via CTEP-AERS within 24 hours of learning of the event followed by a complete CTEP-AERS report within 5 calendar days of the initial 24-hour report.
  - “10 calendar days” - A complete CTEP-AERS report on the AE must be submitted within 10 calendar days of the investigator learning of the event.
- Any medical event equivalent to CTCAE grade 3, 4, or 5 that precipitates hospitalization (or prolongation of existing hospitalization) must be reported regardless of attribution and designation as expected or unexpected with the exception of any events identified as protocol-specific expedited adverse event reporting exclusions.
- Any event that results in persistent or significant disabilities/incapacities, congenital anomalies, or birth defects must be reported via CTEP-AERS if the event occurs following treatment with an agent under a CTEP IND.
- Use the NCI protocol number and the protocol-specific patient ID assigned during trial registration on all reports.

#### **11.1.2 Expedited Adverse Event Reporting Exclusions**

N/A

Note: All deaths on study must be reported using expedited reporting regardless of causality. Attribution to treatment or other cause should be provided.

#### **11.1.3 Secondary AML/MDS**

Investigators are required to report cases of secondary AML/MDS occurring on or following treatment on NCI-sponsored chemotherapy protocols through CTEP-AERS. If Please refer to the CTEP, NCI Guidelines (available at <http://ctep.cancer.gov>) for additional information about secondary AML/MDS reporting.

Second malignancies and non-AML/MDS secondary malignancies (*e.g.*, endometrial cancer in a breast cancer patient receiving tamoxifen) should NOT be reported via CTEP-AERS but should be submitted as part of the study results via routine CDUS reporting.

### **11.2 Data Reporting**

This study will be monitored by the Clinical Data Update System (CDUS) version 3.0. Cumulative CDUS data will be submitted quarterly to CTEP by electronic means. Reports are

due January 31, April 30, July 31, and October 31.

### **11.3 CTEP Multicenter Guidelines**

If an institution wishes to collaborate with other participating institutions in performing a CTEP sponsored research protocol, then the following guidelines must be followed.

#### **Responsibility of the Protocol Chair**

- The Protocol Chair will be the single liaison with the CTEP Protocol and Information Office (PIO). The Protocol Chair is responsible for the coordination, development, submission, and approval of the protocol as well as its subsequent amendments. The protocol must not be rewritten or modified by anyone other than the Protocol Chair. There will be only one version of the protocol, and each participating institution will use that document. The Protocol Chair is responsible for assuring that all participating institutions are using the correct version of the protocol.
- The Protocol Chair is responsible for the overall conduct of the study at all participating institutions and for monitoring its progress. All reporting requirements to CTEP are the responsibility of the Protocol Chair.
- The Protocol Chair is responsible for the timely review of Adverse Events (AE) to assure safety of the patients.
- The Protocol Chair will be responsible for the review of and timely submission of data for study analysis.

#### **Responsibilities of the Coordinating Center**

- Each participating institution will have an appropriate assurance on file with the Office for Human Research Protection (OHRP), NIH. The Coordinating Center is responsible for assuring that each participating institution has an OHRP assurance and must maintain copies of IRB approvals from each participating site.
- Prior to the activation of the protocol at each participating institution, an OHRP form 310 (documentation of IRB approval) must be submitted to the CTEP PIO.
- The Coordinating Center is responsible for central patient registration. The Coordinating Center is responsible for assuring that IRB approval has been obtained at each participating site prior to the first patient registration from that site.
- The Coordinating Center is responsible for the preparation of all submitted data for review by the Protocol Chair.
- The Coordinating Center will maintain documentation of AE reports. There are two options for AE reporting: (1) participating institutions may report directly to CTEP with a copy to the Coordinating Center, or (2) participating institutions report to the Coordinating Center who in turn report to CTEP. The Coordinating Center will submit AE reports to the Protocol Chair for timely review.
- Audits may be accomplished in one of two ways: (1) source documents and research records for selected patients are brought from participating sites to the Coordinating Center for audit, or (2) selected patient records may be audited on-site at participating

sites. If the NCI chooses to have an audit at the Coordinating Center, then the Coordinating Center is responsible for having all source documents, research records, all IRB approval documents, NCI Drug Accountability Record forms, patient registration lists, response assessments scans, x-rays, etc. available for the audit.

#### **Inclusion of Multicenter Guidelines in the Protocol**

- The protocol must include the following minimum information:
  - The title page must include the name and address of each participating institution and the name, telephone number and e-mail address of the responsible investigator at each participating institution.
  - The Coordinating Center must be designated on the title page.
  - Central registration of patients is required. The procedures for registration must be stated in the protocol.
  - Data collection forms should be of a common format. Sample forms should be submitted with the protocol. The frequency and timing of data submission forms to the Coordinating Center should be stated.
  - Describe how AEs will be reported from the participating institutions, either directly to CTEP or through the Coordinating Center.

#### **Agent Ordering**

- Except in very unusual circumstances, each participating institution will order DCTD-supplied investigational agents directly from CTEP. Investigational agents may be ordered by a participating site only after the initial IRB approval for the site has been forwarded by the Coordinating Center to the CTEP PIO.

### **11.4 Cooperative Research and Development Agreement (CRADA)/Clinical Trials Agreement (CTA)**

The agent(s), supplied by CTEP, DCTD, NCI, used in this protocol is/are provided to the NCI under a Collaborative Agreement (CRADA, CTA) between the Merck Pharmaceutical Company [hereinafter referred to as Collaborator] and the NCI Division of Cancer Treatment and Diagnosis. Therefore, the following obligations/guidelines, in addition to the provisions in the Intellectual Property Option to Collaborator contained within the terms of award, apply to the use of Agent(s) in this study:

1. Agent(s) may not be used for any purpose outside the scope of this protocol, nor can Agent(s) be transferred or licensed to any party not participating in the clinical study. Collaborator(s) data for Agent(s) are confidential and proprietary to Collaborator(s) and shall be maintained as such by the investigators. The protocol documents for studies utilizing investigational agents contain confidential information and should not be shared or distributed without the permission of the NCI. If a copy of this protocol is requested by a patient participating on the study or patient's family member, the individual should sign a confidentiality agreement. A suitable model agreement can be downloaded from <http://ctep.cancer.gov>.

2. For a clinical protocol where there is an investigational Agent used in combination with (an)other investigational Agent(s), each the subject of different collaborative agreements, the access to and use of data by each Collaborator shall be as follows (data pertaining to such combination use shall hereinafter be referred to as "Multi-Party Data".):

a. NCI must provide all Collaborators with prior written notice regarding the existence and nature of any agreements governing their collaboration with NIH, the design of the proposed combination protocol, and the existence of any obligations that would tend to restrict NCI's participation in the proposed combination protocol.

b. Each Collaborator shall agree to permit use of the Multi-Party Data from the clinical trial by any other Collaborator solely to the extent necessary to allow said other Collaborator to develop, obtain regulatory approval, or commercialize its own investigational agent.

c. Any Collaborator having the right to use the Multi-Party Data from these trials must agree in writing prior to the commencement of the trials that it will use the Multi-Party Data solely for development, regulatory approval, and commercialization of its own investigational agent.

3. Clinical Trial Data and Results and Raw Data developed under a Collaborative Agreement will be made available exclusively to Collaborator(s), the NCI, and the FDA, as appropriate and unless additional disclosure is required by law or court-order. Additionally, all Clinical Trial Data and Results and Raw Data will be collected, used and disclosed consistent with all applicable federal statutes and regulations for the protection of human subjects, including, if applicable, the Standards for Privacy of Individually Identifiable Health Information set forth in 45 C.F.R. Part 164.

4. When a Collaborator wishes to initiate a data request, the request should first be sent to the NCI, who will then notify the appropriate investigators (Group Chair for Cooperative Group studies, or PI for other studies) of Collaborator's wish to contact them.

5. Any data provided to Collaborator(s) for phase 3 studies must be in accordance with the guidelines and policies of the responsible Data Monitoring Committee (DMC), if there is a DMC for this clinical trial.

6. Any manuscripts reporting the results of this clinical trial must be provided to CTEP for immediate delivery to Collaborator(s) for advisory review and comment prior to submission for publication. Collaborator(s) will have 30 days from the date of receipt for review. Collaborator shall have the right to request that publication be delayed for up to an additional 30 days in order to ensure that Collaborator's confidential and proprietary data, in addition to Collaborator(s)'s intellectual property rights, are protected. Copies of abstracts must be provided to CTEP for forwarding to Collaborator(s) for courtesy review as soon as possible and preferably at least three (3) days prior to submission, but in any case, prior to presentation at the meeting or publication in the proceedings. Press releases and other media presentations must also be forwarded to CTEP prior to release. Copies of any manuscript, abstract, and/or press release/ media presentation should be sent to:

Regulatory Affairs Branch, CTEP, DCTD, NCI  
[name]  
[name]  
[contact]  
E-mail: [[contact]](mailto:[contact])

The Regulatory Affairs Branch will then distribute them to Collaborator(s). No publication, manuscript or other form of public disclosure shall contain any of Collaborator's confidential/proprietary information.

## 12. STATISTICAL CONSIDERATIONS

### 12.1 Study Design/Endpoints

#### 12.1.1. Study Design:

We will use a 2-stage Simon (1989) optimal design to minimize the number of patients to be treated. Complete + partial (CR+PR) rate will be the primary statistical endpoint. We wish to distinguish response rate regions of at most 5% vs. at least 20%. For this 2-stage design its Stage 1 will require 12 response-evaluable (r-e) patients. At least 1 responder in Stage 1 will be needed to justify continuing to Stage 2, which will require 17 more r-e patients (i.e., maximum of N=29 r-e patients for the study). If  $\geq 3$  responders are observed among the final 29 r-e patients, then vorinostat will be considered promising. If  $< 3$ , conclude that vorinostat has insufficient efficacy to justify further study. This design specifies significance level = 0.15, and power = 0.90, and has a probability of early termination (PET) = 0.540 under the null hypothesis. Alpha is relaxed in this design since there are no effective therapies available, but beta is limited to 0.10 to better ensure that we identify vorinostat as a promising therapy, if it truly is one.

In ACC, late responses (by RECIST) may occur; hence we anticipate the need to suspend accrual after 12 r-e patients have been enrolled for Stage 1. Among stable disease patients still on vorinostat treatment, responses could occur as long as one year after treatment started. Should vorinostat have little efficacy, disease progression among the Stage 1 patients will be more rapid, thus limiting the time until study termination can be justified based on the Stage 1 response results.

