#### 10.1.1 Definitions

Evaluable for toxicity. All patients will be evaluable for toxicity from the time of their first treatment with vorinostat.

Evaluable for objective response. Only those patients who have measurable disease present at baseline, have received at least one cycle of therapy, and have had their disease re-evaluated will be considered evaluable for response. These patients will have their response classified according to the definitions stated below. (Note: Patients who exhibit objective disease progression prior to the end of cycle 1 will also be considered evaluable.)

Evaluable Non-Target Disease Response. Patients who have lesions present at baseline that are evaluable but do not meet the definitions of measurable disease, have received at least one cycle of therapy, and have had their disease re-evaluated will be considered evaluable for non-target disease. The response assessment is based on the presence, absence, or unequivocal progression of the lesions.

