### **12.5.2 Evaluation of Response.**

All patients included in the study must be assessed for response to treatment, even if there are major protocol treatment deviations or if they are ineligible. Each patient will be assigned one of the following categories: 1) complete response, 2) partial response, 3) stable disease, 4) progressive disease, 5) early death from malignant disease, 6) early death from toxicity, 7) early death because of other cause, or 9) unknown (not assessable, insufficient data). [Note: By arbitrary convention, category 9 usually designates the “unknown” status of any type of data in a clinical database.]

All of the patients who met the eligibility criteria (with the possible exception of those who received no study medication) should be included in the main analysis of the response rate. Patients in response categories 4-9 should be considered as failing to respond to treatment (disease progression). Thus, an incorrect treatment schedule or drug administration does not

result in exclusion from the analysis of the response rate. Precise definitions for categories 4-9 will be protocol specific.

All conclusions should be based on all eligible patients. Sub-analyses may then be performed on the basis of a subset of patients, excluding those for whom major protocol deviations have been identified (e.g., early death due to other reasons, early discontinuation of treatment, major protocol violations, etc.). However, these sub-analyses may not serve as the basis for drawing conclusions concerning treatment efficacy, and the reasons for excluding patients from the analysis should be clearly reported. The 95% confidence intervals should also be provided.

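### The primary denominator is contradictory: the Simon decision rule counts response-evaluable patients, while Section 12.5.2 requires conclusions on all eligible patients

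*Combined protocol and SAP*

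**What the plan says.** Section 12.1.1 specifies a Simon optimal two-stage design to separate a response rate of at most 5% from one of at least 20%, with significance level 0.15, power 0.90 and probability of early termination (PET) 0.540 under the null. Both cut-offs are applied to response-evaluable patients. For the first stage, "Stage 1 will require 12 response-evaluable (r-e) patients", and "At least 1 responder in Stage 1 will be needed to justify continuing to Stage 2". At the end, the test is whether three or more "responders are observed among the final 29 r-e patients, then vorinostat will be considered promising".

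Section 10.1.1 defines that set. Besides having measurable disease at baseline, patients must "have received at least one cycle of therapy, and have had their disease re-evaluated will be considered evaluable for response". One exception is made: objective progression before the end of cycle 1 also makes a patient evaluable.

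Section 12.5.2 takes another population. Patients who met the eligibility criteria, possibly except those never treated, belong in the main response-rate analysis. Early deaths and the unknown category are handled thus: "Patients in response categories 4-9 should be considered as failing to respond to treatment (disease progression"). It then states: "All conclusions should be based on all eligible patients". Analyses that leave out patients with, for example, early death or early discontinuation are sub-analyses, and these may not support efficacy conclusions.

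Neither section refers to the other. No non-evaluable rate is given, and there is no replacement rule.

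**The concern.** A treated, eligible patient who stops in cycle 1 for toxicity or withdrawal, or who dies without a repeat scan, is outside the denominator in Section 12.1.1 but is a failure in the denominator of Section 12.5.2. Such patients can only lower the response rate, so the two sections can give different answers from the same data. With 3 responders, 29 response-evaluable and 33 eligible patients, Section 12.1.1 calls the drug promising (3/29 = 10.3%). Section 12.5.2 reports 3/33 = 9.1% and has no cut-off to judge it by.

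This is the primary endpoint and the trial's only efficacy decision. If the sections stay unreconciled, the denominator could be chosen after the result is seen. The error rates are also affected, because the plan does not say to which population the 5% and 20% belong.

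**Working it through.** **Inputs.** From Section 12.1.1: p0 = 0.05, p1 = 0.20, n1 = 12, total n = 29 (17 more in stage 2), continue with at least 1 responder, promising with at least 3. The share f of eligible patients who are non-evaluable is not in the documents; 5 to 20% is an assumption. The accrual timing in Section 12.2 allows for no loss: 12 to 24 patients a year are to give 12 response-evaluable patients in 6 to 12 months.

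**Step 1: reproduce the stated figures.** Let X be the responders among the first 12 and Y those among the next 17, both binomial with rate p.

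PET = (1 − p)^12

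P(promising) = P(X=1)·P(Y≥2) + P(X=2)·P(Y≥1) + P(X≥3)

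- p = 0.05: PET = 0.95^12 = 0.540. Alpha = 0.3413 × 0.2078 + 0.0988 × 0.5819 + 0.0196 = 0.148.
- p = 0.20: power = 0.2062 × 0.8818 + 0.2835 × 0.9775 + 0.4417 = 0.9005 (from unrounded terms).

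The expected sample size under the null is 12 + 17 × (1 − 0.540) = 19.8. A search over designs with alpha at most 0.15 and power at least 0.90 returns this design as the one with the smallest expected size. The stated 0.15 is the design limit and 0.148 is what the discrete rule attains. The design is correct for the population it names.

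**Step 2: response-evaluable rule, null defined on eligible patients.** Suppose a share f of eligible patients is non-evaluable, none of them responds, and enrolment continues until 12 and then 29 are evaluable. A 5% rate among eligible patients becomes 0.05/(1 − f) among evaluable patients. At f = 10% this is 0.05/0.90 = 0.0556, and alpha = 0.3555 × 0.2431 + 0.1150 × 0.6216 + 0.0258 = 0.184.

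**Step 3: fixed 12 and 29 eligible patients, non-evaluable counted as failures.** If 5% and 20% are rates among eligible patients, step 1 applies unchanged. If they are rates among evaluable patients, they shrink to 0.05(1 − f) and 0.20(1 − f).

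| Assumed f | Step 2: rate among evaluable | Step 2: alpha | Step 2: mean eligible needed, 29/(1 − f) | Step 3, evaluable rates: alpha | Step 3, evaluable rates: power |
|---|---|---|---|---|---|
| 0% | 5.0% | 0.148 | 29 | 0.148 | 0.9005 |
| 5% | 5.3% | 0.165 | 30.5 | 0.133 | 0.881 |
| 10% | 5.6% | 0.184 | 32.2 | 0.118 | 0.858 |
| 15% | 5.9% | 0.206 | 34.1 | 0.104 | 0.831 |
| 20% | 6.3% | 0.231 | 36.2 | 0.091 | 0.800 |

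Under the premises of step 2, alpha passes 0.15 once f exceeds about 0.65%.

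**Step 4: who is lost.** The first mandatory on-treatment scan is at day 56 (Schema, Treatment Period). However, the Schema's Post-treatment Period asks for imaging at the end-of-study visit, within 30 days of the last dose, if none was done in the previous 30 days. Section 9 lists an off-study tumor measurement. A patient who completes cycle 1 and then stops should therefore usually be re-scanned and be evaluable. The losses are mainly patients who stop within cycle 1 without objective progression, or who are never re-scanned.

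**The case against.** A reader might infer that the 0.15 error rate is simply wrong. The documents do not support that. Section 12.1.1 gives the 5% and 20% alongside response-evaluable sample sizes and never ties them to all eligible patients. If they are rates among evaluable patients, there is no inflation. Inflation needs both a null defined on eligible patients and losses that are replaced. Replacement is implied by requiring 12 and 29 evaluable patients, but it is not stated.

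Elsewhere the plan treats 12 and 29 as the whole study: the accrual table in Section 12.3.1 totals 12/29 subjects, and Section 12.4 uses n = 12 and n = 29 for toxicity, for which every treated patient counts. That suggests the two sets were assumed to be the same size and that an allowance for loss was overlooked, rather than a deliberate exclusion. If enrolment stops at 29 and drop-outs count as failures, alpha does not exceed 0.148.

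Two further points stand. Section 12.1.1 deliberately relaxes alpha and limits beta to 0.10, so a fix that costs power touches the error the design set out to protect. And Section 8 and Appendix D already report two partial responses, so changing the denominator now means changing it after outcomes are known. It would be tempting to add that the choice of denominator has already decided the result. That does not follow: two is below three on either denominator, and the documents do not give the accrual status at that point.

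None of this removes the contradiction. Even if the two sets were expected to coincide, the plan gives opposite instructions for the first patient who falls in one and not the other.

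**Conclusion.** The contradiction stands on the text alone and needs correction, because it concerns the primary analysis population and the only go/no-go rule. The stated operating characteristics are right for response-evaluable patients (0.148, 0.9005, 0.540) and are shown for that set only. The rise in alpha to between 0.165 and 0.231 is conditional: it assumes a 5% null on all eligible patients, replacement of non-evaluable patients, no responders among them, and a loss of 5 to 20%. The documents supply no loss rate, and the off-study imaging requirement narrows who can be lost. It should be reported as a range under assumptions, not as an error in the stated 0.15.

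**What to change.** In Sections 12.1.1, 12.2, 10.1.1 and 12.5.2, name one primary population for both the decision rule and the main analysis. The preferred choice is eligible patients who received at least one dose of vorinostat:

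- Define the 12 and the 29 in that population.
- Count anyone without a confirmed CR or PR, including categories 4-9, as a non-responder at both stages.
- State that the 5% and 20% apply to that population. The stated alpha, power and PET then hold as written.
- Keep the Section 10.1.1 definition for a labelled response-evaluable sub-analysis that does not drive the decision.

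The change is one of wording and needs no extra patients. Its possible cost is power: if 20% is really the rate among evaluable patients, power is 0.881, 0.858, 0.831 or 0.800 at 5, 10, 15 or 20% loss, against a target of 0.90. The sponsor should accept that openly or revisit the sample size.

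Because two partial responses are already reported, fix the population before the final analysis, record that the change was made after those responses were known, and report the response rate on both denominators.
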